### 1.4.1 Weekly Dosing: Dose Escalation Results

The weekly dosing regimen dose escalation included dose levels from 5 ng/kg up to 900 ng/kg, and the MTD for this dosing regimen was identified at 600 ng/kg QW (Middleton, 2015). In the review of the safety and pharmacokinetic (PK) data for the weekly dosing regimen, the RP2D-QW was initially identified as a flat dose of 50 mcg administered intravenously (IV) on a weekly basis; [REDACTED]

[REDACTED]

[REDACTED]

[REDACTED]

[REDACTED]

Cytokine analyses of the peripheral circulation combined with clinical findings in patients treated with weekly dosing revealed rare cases of severe, systemic cytokine release syndrome. As a consequence of on-target skin or tumor activity, with consequential cytokines permeating into the periphery, many patients showed modest, drug-induced levels of 1 or more inflammatory cytokines [REDACTED]

[REDACTED]

Please refer to the current IMCgp100 Investigator’s Brochure for details.

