### 6.5 Management and Follow-up of Toxicity

Patients whose study treatment is interrupted or permanently discontinued due to an AE or clinically significant laboratory value, must be followed-up at least once a week (or more if clinically indicated) for 4 weeks, and subsequently at approximately 4-week intervals, until resolution or stabilization of the event, whichever comes first. Appropriate clinical experts should be consulted as deemed necessary for any AEs

observed in the course of the trial. In the case of a toxicity suspected to be related to a cytokine release syndrome, the immunologic assessments outlined in [Section 7.3.4](#) should be performed.

Guidelines for management of AE and dose modifications are presented below in [Table 6-2](#) (below). Institutional protocols for management of immune-related AEs should be implemented in cases of immune-related AEs and will take precedence over guidance in [Table 6-2](#). All patients must be followed up for the occurrence of AEs and SAEs for 90 days following the last dose of IMCgp100.

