**Table 6-2 Recommended Dose Modifications by Toxicity Grade for Study Medications**

Worst Toxicity NCI CTCAE v4.03 Grade	Recommended Dose Modifications
Grade 2	Intravenous fluid support and other supportive measures for additional AE as needed.
Grade 3 or 4	Hold all doses of IMCgp100 until returned to NCI CTCAE grade $\leq$ 1. Intravenous fluid support and other supportive measures for additional adverse events. In cases of hypotension where fluid support is not adequate, consider systemic corticosteroid therapy as needed for hypotension. In case of hypotension not responding to intravenous corticosteroid, inotropic pressor support may be indicated.
Cytokine Release Syndrome	
Grade 2	Interrupt infusion of IMCgp100. Supportive measures for symptoms of cytokine release, ie, intravenous fluid support, non-steroidal anti-inflammatory drug (NSAID), antihistamine. If resolves within 4 hours, may restart infusion of IMCgp100. If recurs with restarting infusion, hold the dose of IMCgp100 and institute supportive measures as indicated.
Grade 3	Discontinue infusion immediately. Supportive measures for symptoms of cytokine release, ie, intravenous fluid support, NSAID, antihistamine. To consider intravenous corticosteroid (eg, methylprednisolone or hydrocortisone) for severe symptoms and management of sequelae. If symptoms resolve to NCI CTCAE grade 1 within 7 days, may consider restarting IMCgp100 after written approval of Sponsor Medical Monitor.
Grade 4	Discontinue infusion immediately. Supportive measures for symptoms of cytokine release. In addition to supportive measures, intravenous corticosteroid dosing (eg, methylprednisolone or hydrocortisone) should be administered. If symptoms do not resolve with intravenous corticosteroid dosing consider anti-IL6 (tocilizumab) therapy. If symptoms resolve to NCI CTCAE grade 1 within 7 days, may consider restarting IMCgp100 after written approval of Sponsor Medical Monitor.
Other Adverse Events	
In patients experiencing adverse events (not meeting the specific criteria above) of grade $\geq$ 3, study drugs should be omitted until resolved to grade $\leq$ 1. Treat according to institutional practice and for immune-related adverse events of grade 3 or greater, treatment with corticosteroids should be considered. Consult Sponsor Medical Monitor for further guidance as needed.	

NCI CTCAE = National Cancer Institute Common Terminology Criteria for Adverse Events; NSAID = non-steroidal anti-inflammatory drug.

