## 6.6 Treatment Discontinuation

Reasons for discontinuation of study treatment will include:

- Unequivocal PD, see [Section 6.6.1](#)
- Loss of clinical benefit from treatment with IMCgp100 in the opinion of the principal investigator or the initiation of alternative anti-cancer therapy (including another investigational agent)
- Unacceptable toxicity defined as an AE that, in the opinion of the investigator or the Sponsor, contraindicates further dosing, including  $\geq$  grade 3 cytokine release syndrome
- Withdrawal of consent from further treatment with investigational product by the patient or the investigator or lost to follow-up
- Patient is determined to have failed to meet selection criteria for the study AND continuing to receive investigational product might constitute a safety risk. Patients who fall into this category and for whom continuation of study treatment is not thought to pose a safety risk in the opinion of the investigator may continue to receive study treatment after discussion with the Sponsor
- Pregnancy or intent to become pregnant

At the time patients discontinue study treatment, the EOT visit should be scheduled in the appropriate window of 14 days after the last dose was administered. At this visit, all of the assessments listed for the EOT visit will be performed (see [Table 7-1](#)). If the decision to withdraw the patient occurs at a regularly scheduled visit, that visit may become the EOT visit rather than having the patient return for an additional visit (EOT follow-up will still continue for the full 14-day observation period, see [Section 7.2](#) for details of assessments required). An End of Treatment eCRF page should be completed at the EOT visit, giving the date and reason for stopping the study treatment. End of treatment/premature withdrawal visit is not considered as the end of the study.

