13.1. Study Drug Exposure Derivations

A cycle is defined as 28 days = 4 weeks, and at least 1 dose administration visit per cycle for each of the treatment regimen for IMCgp100 (doses are given every week).

The following will be derived:

- *Number of cycles started* = total number of cycles of study drug received (including partial cycles), during the rollover study
- *Number of cycles completed* = total number of complete cycles of study drug received without any interruption, during the rollover study
- *Total planned dose* = sum of the total dose levels that a patient planned to receive during the rollover study, up to the date of last study drug administration
- *Duration of treatment (days)* = (date of last study drug administration – date of first study drug administration in the rollover study + 1). Note that this calculation does not include any post dose rest period. *Duration of treatment from first parent study dose (days)* = (date of last study drug administration – date of first parent study dose of IMCgp100 + 1). Note that this calculation does not include any post dose rest period
- *Duration of interruption (days)* = (start date of next study drug administration following interruption - date of visit in which interruption started). Note that this is calculated for each interruption a given patient has and is only calculated where study drug administration restarts following interruption.
 - “Date of visit in which interruption started” = ‘date of visit’ from the *Date of Visit* eCRF pages, where the visit may also be a visit classified as “not done”. If it is clear that an interruption to dosing has occurred, but no *Date of Visit* eCRF page nor *Administration of Study Drug* eCRF page is entered at least 14 days (i.e. at least 7 days ± 7 day visit window) following the previous dosing visit, where dosing would have been expected, then the date of the *expected* next dose following last administered dose, may be used instead (=previous ‘start date of study drug administration’ + 14 days). See the definition of a *dose interruption* below.
 - If a patient does not have a “start date of *next* study drug administration following interruption” then a dose interruption is not counted because either:
 - The Date of study drug discontinuation from the *End of Treatment* page of the eCRF is filled out, in which case the study drug was discontinued rather than interrupted, or

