- d. The *total planned dose* is based on either the 'Parent Study Dose IMCgp100', or if applicable, the dose entered in 'Was dose changed from parent study' item, on the *Parent Study Details -IMCgp100* eCRF page. This planned dose is summed up over all visits where a patient planned to receive study drug, even if the said dose is actually missed during the visit, up until the cut-off as described above. This calculation is necessary for the planned dose intensity, which is used to calculate the relative dose intensity.
- e. The *total actual dose received* is based on the 'Actual dose administered' entered on the *Administration of Study Drug* eCRF for each visit administration of study drug. The actual dose administered is summed up over all visits where a patient actually received study drug, up until the cut-off as described above.
- f. The date of first study drug administration is taken from the earliest 'Dose start date' entered on the eCRF.
- g. The date of last study drug administration is taken from the latest 'Dose end date'

entered on the eCRF.

Definitions of Dose Interruption:

Dose interruption – an entire dosing visit is skipped or entered as omitted in the eCRF. To clarify, if a dose on a single day is restarted and partial or entire dose is still taken, then this is not a dose interruption. Dose interruptions will be flagged on the *Administration of Study Drug* eCRF page where the response to ‘*Did the patient receive investigational product at this visit?*’ is equal to ‘*No, reason for dose omission*’. Also, dose interruptions are counted in cases where a patient misses an entire study visit, where dosing is expected.

A single interruption is defined as any length of time a patient misses dosing visits. For example, for IMCgp100 which is administered weekly, then a single dose interruption would be defined regardless of whether only 1 week was missed or 2 consecutive weeks dosing were missed.

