15.1.2. TEAEs Leading to Discontinuation of Study Drug

TEAEs leading to permanent discontinuation of study drug will be identified by using the ‘Action taken with the study drug’ variable collected on the eCRF, where the variable is equal to ‘Drug permanently discontinued’. These will be flagged in the listing.

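### Protocol Section 6.6 lists grade 3 or higher cytokine release syndrome as a reason to stop IMCgp100, while Table 6-2 allows a Sponsor-approved restart, and no readable text says which governs

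*Protocol*

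**What the plan says.** Protocol Section 6.6 lists the reasons for discontinuing study treatment. Its third bullet reads "Unacceptable toxicity defined as an AE that, in the opinion of the investigator or the Sponsor, contraindicates further dosing, including" and then names, after a greater-than-or-equal sign, "grade 3 cytokine release syndrome". The bullet gives no exception for an event that resolves and does not refer to Table 6-2.

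Table 6-2 has its own CRS rows. At grades 3 and 4 the infusion is discontinued immediately and supportive treatment given. Both rows then end with the same sentence: "If symptoms resolve to NCI CTCAE grade 1 within 7 days, may consider restarting IMCgp100 after written approval of Sponsor Medical Monitor".

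The only ranking statement attached to Table 6-2 is in Section 6.5: "Institutional protocols for management of immune-related AEs should be implemented in cases of immune-related AEs and will take precedence over guidance in" the table. It concerns institutional protocols and says nothing about Section 6.6.

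**The concern.** For one well-defined event, grade 3 or 4 CRS that settles to grade 1 within 7 days, one section names a stop and the other opens a route to further dosing. Re-exposure after a severe or life-threatening reaction should not depend on which page the site consults.

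Harm is possible in both directions. A site working from Table 6-2 may ask to re-dose after an event that Section 6.6 classes as contraindicating further dosing. A site working from Section 6.6 may permanently stop a patient who entered the study because of continuing benefit and lack of alternatives (Section 2.2), without making the request that the table allows.

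The choice also carries into the tolerability results, because the SAP records a stop and a restart differently.

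**Working it through.** No figure in the plan is in dispute. The check compares the texts and then traces one event through the SAP's counting rules.

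**The two rules by event**

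| Event | Section 6.6 | Table 6-2, CRS rows | Agree? |
|---|---|---|---|
| Grade 3 or 4, not resolved to grade 1 within 7 days | Reason to discontinue | No restart route | Yes |
| Grade 3 or 4, resolved in time, restart not approved | Reason to discontinue | No restart | Yes |
| Grade 3 or 4, resolved in time, restart approved in writing | Reason to discontinue | Restart may be considered | **No** |

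**Does any other text settle it?**

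- Section 6.5 ranks institutional protocols above Table 6-2 for immune-related events only.
- Section 6.6.1, criterion 2, treats the Section 6.6 list as discontinuation criteria and adds no exception.
- Sections 3.1 and 3.3 end treatment at unacceptable toxicity as the investigator or Sponsor defines it. They mention neither CRS nor Table 6-2.
- Section 7.2.2 refers back to Section 6.6.
- The SAP does not address the point.

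The drafting shows that an exception could have been written. In the same Section 6.6 list, the first bullet cross-refers to Section 6.6.1, and the fifth spells out when an ineligible patient may stay on treatment after discussion with the Sponsor. Table 6-2 states permanent discontinuation where it intends it, for grade 4 rash and grade 3 or 4 infusion reactions. Its CRS rows are therefore a different rule.

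**One such event through the SAP**

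Inputs:

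- SAP 15.1.2: "TEAEs leading to permanent discontinuation of study drug will be identified by using the" action-taken field of the eCRF, where it records permanent discontinuation.
- SAP 13.1: an interruption means that "an entire dosing visit is skipped or entered as omitted in the eCRF". If no later dose is given, "then a dose interruption is not counted because either" the drug was discontinued or the outcome is still unknown.
- SAP 15.1: an adverse event starting between the first rollover dose and 90 days after the last dose is treatment-emergent.

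| Course, weekly dosing | Discontinuation flag | Interruptions | CRS counted as treatment-emergent |
|---|---|---|---|
| Permanent stop | 1 | 0 | 1 |
| Restart, next weekly visit dosed | 0 | 0 | 1 |
| Restart after at least one whole visit missed | 0 | 1 | 1 |

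Stop minus restart:

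- Flag: 1 − 0 = 1 per event.
- Interruptions: 0 − 0 = 0 or 0 − 1 = −1, an absolute difference of 0 or 1.
- Index event as treatment-emergent: 1 − 1 = 0.

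With k such events, of which r are restarted (0 ≤ r ≤ k), the flagged count is k − r. It therefore runs from k down to 0, a possible difference of 0 to k.

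**How large is k?** The documents give no readable rate. Protocol Section 1.4.1 says that findings under weekly dosing "revealed rare cases of severe, systemic cytokine release syndrome".

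**The case against.** The strongest reply is that the two texts can be read together. The test in Section 6.6 is the opinion of the investigator or Sponsor, and Sections 3.1 and 3.3 use the same idea. Written Medical Monitor approval under Table 6-2 would then be the Sponsor's opinion that dosing is not contraindicated: CRS of grade 3 or higher is presumed unacceptable, and the table gives the procedure for deciding otherwise. Section 6.6 also lacks the explicit permanent-stop wording used for grade 4 rash and severe infusion reactions.

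This reading is plausible and may be what was intended, but it is written nowhere. Other cues point the opposite way: Section 6.5 introduces the table as guidelines and its title calls the modifications recommended, which favours Section 6.6. A site should not have to infer a rechallenge rule.

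Other parts of the reply stand:

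- No site can restart on its own authority, and one that stops permanently complies with both texts.
- The SAP rules work correctly under either course; the differing counts are a consequence of the ambiguity, not an SAP error.
- There is no hypothesis test to disturb.
- The description of severe CRS as rare comes from a section on escalation up to 900 ng/kg, above the 600 ng/kg MTD, so it gives no rate for this population.
- The zero difference in treatment-emergent counts covers the index event only. A restarted patient could have later events.

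**Conclusion.** The concern holds. Section 6.6 and Table 6-2 give different answers on re-exposure after grade 3 or 4 CRS that resolves to grade 1 within 7 days, and no readable text reconciles them. It should be fixed because it is a safety instruction for a severe or life-threatening event, even though few patients are likely to be affected and written approval limits the risk.

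The effect on results is modest: one discontinuation flag and at most one dose interruption per event, with the primary variable not directly changed. This assumes that the eCRF action-taken field records what was done. It also rests on the readable text, since parts of Sections 6.1 and 6.2.3 are redacted.

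**What to change.** State one rule. The lighter change is to qualify the CRS example in the third bullet of Section 6.6: it applies unless the event has resolved to grade 1 within 7 days and the Sponsor Medical Monitor has approved restart in writing under Table 6-2.

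If the sponsor instead wants no re-exposure at grade 3, grade 4 or both, the corresponding Table 6-2 rows should say that treatment is permanently discontinued, and the Section 6.6 bullet should match. That is a clinical decision for the sponsor and would change the rule, not merely clarify it.

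Section 6.6.1 needs no edit, because its second criterion already refers to Section 6.6. The cost is one clause or up to two table rows, plus whatever ethics review the protocol change requires. It needs no new data and no SAP change.

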## 6.6 Treatment Discontinuation

Reasons for discontinuation of study treatment will include:

- Unequivocal PD, see [Section 6.6.1](#)
- Loss of clinical benefit from treatment with IMCgp100 in the opinion of the principal investigator or the initiation of alternative anti-cancer therapy (including another investigational agent)
- Unacceptable toxicity defined as an AE that, in the opinion of the investigator or the Sponsor, contraindicates further dosing, including  $\geq$  grade 3 cytokine release syndrome
- Withdrawal of consent from further treatment with investigational product by the patient or the investigator or lost to follow-up
- Patient is determined to have failed to meet selection criteria for the study AND continuing to receive investigational product might constitute a safety risk. Patients who fall into this category and for whom continuation of study treatment is not thought to pose a safety risk in the opinion of the investigator may continue to receive study treatment after discussion with the Sponsor
- Pregnancy or intent to become pregnant

At the time patients discontinue study treatment, the EOT visit should be scheduled in the appropriate window of 14 days after the last dose was administered. At this visit, all of the assessments listed for the EOT visit will be performed (see [Table 7-1](#)). If the decision to withdraw the patient occurs at a regularly scheduled visit, that visit may become the EOT visit rather than having the patient return for an additional visit (EOT follow-up will still continue for the full 14-day observation period, see [Section 7.2](#) for details of assessments required). An End of Treatment eCRF page should be completed at the EOT visit, giving the date and reason for stopping the study treatment. End of treatment/premature withdrawal visit is not considered as the end of the study.

### 6.6.1 Criteria for Treatment Beyond Initial RECIST v.1.1 Disease Progression

Imaging studies will be performed on all patients to monitor for disease progression using RECIST v1.1 criteria. Upon disease progression by standard RECIST v.1.1 criteria, treatment beyond progression is an option.

Clinical evidence suggests that a minority of patients treated with immunotherapies, including IMCgp100, will derive clinical benefit after an initial assessment of PD. For patients in the IMCgp100 arm, if PD based on RECIST v.1.1 occurs, treatment may continue according to the protocol-specified regimen until 1 of the following criteria is met:

1. Unequivocal, confirmed PD based on immune-related Response Evaluation Criteria in Solid Tumors (irRECIST) (guidelines based on Wolchok, 2009; Nishino, 2013; and Bohnsack, 2014): An initial assessment of PD by RECIST v.1.1 (initial PD assessment) will be confirmed with a repeat radiologic evaluation will be performed at least 4 but no more than 12 weeks later as scheduled per protocol. For patients who continue IMCgp100 therapy beyond initial PD, unequivocal, confirmed PD is defined as an additional 20% increase in tumor burden (sum of diameters of both target and new lesions) from the initial PD assessment
2. Meets any of the investigational product discontinuation criteria ([Section 6.6](#) above)
3. Clinical symptoms or signs indicating clinically significant PD (not meeting radiologic PD) such as decline in ECOG performance status or the benefit-risk ratio of continuing therapy is no longer justified
4. Rapid PD or threat to vital organs/critical anatomical sites (eg, spinal cord compression) requiring urgent alternative medical intervention, and/or continuation of study therapy would prevent institution of such intervention

Once unequivocal, confirmed PD is recognized, treatment with IMCgp100 must be discontinued.

Patients continuing treatment beyond the protocol-specified RECIST v.1.1 progression must provide separate consent to continue treatment after an initial assessment of PD. Treatment and assessments after an initial assessment of PD will continue to follow the treatment regimen of weekly IMCgp100.

## 6.7 Contraception

Women of child-bearing potential, defined as all women physiologically capable of becoming pregnant, unless they are using highly effective methods of contraception during dosing and for 6 months after the last dose of IMCgp100.

Highly effective contraception methods include and of the following:

- Total abstinence from sexual relations for the duration of the treatment when applicable to the lifestyle of the patient. Periodic abstinence (eg, calendar, ovulation, symptothermal, post-ovulation methods) and withdrawal are not acceptable methods of contraception
- Female sterilization (have had surgical bilateral oophorectomy with or without hysterectomy) or tubal ligation at least 6 weeks before taking study treatment. In case of oophorectomy alone, only when the reproductive status of the woman has been confirmed by follow-up hormone level assessment

- Male sterilization (at least 6 months prior to screening). For female patients on the study the vasectomized male partner should be the sole partner for that patient
- The combination of any 2 of the following methods as long as they are both used simultaneously:
  - a. Use of oral, injected, or implanted hormonal methods of contraception or other forms of hormonal contraception that have comparable efficacy (failure rate < 1%), for example hormone vaginal ring or transdermal hormone contraception
  - b. Placement of an intrauterine device or intrauterine system
  - c. Barrier methods of contraception: condom or occlusive cap (diaphragm or cervical/vault caps) when used with spermicidal foam, gel, film, cream, or used of a spermicidal vaginal suppository

In case of use of oral contraception women should have been stable on the same oral contraceptive pill for a minimum of 3 months before beginning treatment on this study.

Women are considered post-menopausal and not of child bearing potential if they have had 12 months of natural (spontaneous) amenorrhea with an appropriate clinical profile (eg, age appropriate, history of vasomotor symptoms) or have had surgical bilateral oophorectomy (with or without hysterectomy) or tubal ligation at least 6 weeks ago. In the case of oophorectomy alone, only when the reproductive status of the woman has been confirmed by follow-up hormone level assessment is she considered not of child bearing potential.

